3.6.1.1 Study CAIN457F2305 in ankylosing spondylitis (AS)

This 104-week, double-blind, placebo-controlled study randomized 371 patients with moderate to severe ankylosing spondylitis (AS) despite current or previous NSAIDs, DMARDs and/or TNF-α inhibitor therapy to 10mg/kg IV load (baseline, Week 2, and Week 4)-75 mg sc every 4 wks maintenance (n=124); IV load regimen-150 mg sc maintenance (n=125), or to placebo IV load and sc maintenance (n=122). At Week 16, non-responder placebo pts would be randomized to 75mg or 150mg maintenance dose without a loading regimen and all remaining (responder) placebo pts would be randomized to 75mg or 150 mg maintenance regimen at Week 24. The primary objective was superiority to placebo based on Assessment of Spondyloarthritis International Society criteria (ASAS) 20 response rate at week 16.

An interim analysis with a cut-off date of 10-Dec-2013 was performed and included efficacy data up to Week 52 and all safety data up to that cut-off date of the study for all patients (regardless of study visit at that time). Over the entire treatment period at time of the data cut-off, the median duration of exposure was 475 days for any 75 mg group and 463 days for any 150 mg group.

Both secukinumab arms were superior to placebo for the primary endpoint of ASAS 20 response at Week16: 59.7% for IV-75 mg and 60.8% for IV-150 mg (p<0.0001) vs. 28.7% for placebo. Additionally, both secukinumab IV-75 mg and IV-150 mg groups were superior to placebo at Week 16 for all endpoints tested in the hierarchical testing strategy. Among those, ASAS 40 response was 33.1% (p=0.0003) for IV-75 mg and 41.6% (p<0.0001) for IV-150 mg compared with 13.1% for placebo and significantly lower ratios of post-baseline to baseline hsCRP values for IV-75 (0.45) and IV-150 mg (0.40) vs. placebo (0.97) were reported (both comparisons, p<0.0001).

Secukinumab was efficacious through 16 weeks of treatment in both anti-TNF- α naive patients and patients with an inadequate response or intolerance to prior anti-TNF- α therapy. ASAS 20 and ASAS 40 response rates for secukinumab vs. placebo observed for TNF- α inhibitor naive pts were numerically higher (ASAS 20 (60.0% and 66.3%) and ASAS 40 (34.4% and 48.9%)) than for TNF- α inhibitor inadequate responders (ASAS 20: 58.8% and 45.5%; ASAS 40: 29.4% and 21.2%) for the IV-75 mg and IV-150 mg regimens, respectively.

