Continuous variables (e.g. change from baseline in BASDAI question 2) will be evaluated using a MMRM with treatment regimen and analysis visit as factors and weight and baseline score as continuous covariates. Treatment by analysis visit and baseline by analysis visit will be included as interaction terms in the model. An unstructured covariance structure will be assumed for this model. The significance of the treatment effects for Secukinumab regimens at different analysis visits will be determined from the pairwise comparisons performed between Secukinumab regimens and placebo and/or Secukinumab at the appropriate analysis visits.

9.5.2 **Exploratory efficacy variables**

The exploratory efficacy variables are listed below. Exploratory efficacy variables will be analyzed using the FAS population.

- Total ASAS-NSAID [Area Under Curve (AUC)] Score from treatment start with Secukinumab to a Secukinumab exposure of 12 weeks.
- Total ASAS-NSAID [Area Under Curve (AUC)] Score From Week 4 to Week 16
- Proportion of patients with no NSAID intake after Secukinumab exposure of 12 weeks
- Proportion of patients with no NSAID intake at week 12.
- Change from Baseline in the ASAS Health Index after Secukinumab exposure of 12 weeks
- Change from Baseline in the ASAS Health Index at week 12
- Change from baseline in BASMI
- ASAS40 response
- ASAS20 response
- ASAS5/6 response
- Change from baseline in hsCRP
- Change from baseline in total BASDAI
- BASDAI 50 response
- ASAS partial remission
- Change from baseline in ASAS components including:
 - a. Patient global disease activity
 - b. Total spinal pain
 - c. Inflammation (average of BASDAI questions 5 and 6)
 - d. BASFI
- Change from baseline in ASDAS-CRP and ASDAS-ESR
- ASDAS inactive disease as defined by ASDAS < 1.3
- ASDAS clinically important improvement (change in ASDAS ≥ 1.1) and major improvement (change in ASDAS ≥ 2.0)
- Reasons given in the patient diary on why he was not able to taper NSAIDs despite reduced spinal pain

Secukinumab groups at week 12 (delayed tapering) and week 16 (early tapering) will be compared for all primary, secondary and exploratory variables that have not been outlined. Variables such as hsCRP whose distribution is not anticipated to be normal will be transformed and analyzed on the loge scale. All other details and analyses regarding the exploratory efficacy variables will be outlined in the statistical analysis plan.

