To explore the efficacy of Secukinumab 150 mg s.c. based on ASAS Health Index after Secukinumab exposure of 12 weeks.	Mean change from Baseline in the ASAS Health Index at week 12 for secukinumab 150 mg s.c. (delayed tapering) and at week 16 for secukinumab 150 mg s.c. (early tapering).
To explore the efficacy of Secukinumab 150 mg s.c. assessed by ASAS Health Index at week 12.	Mean change from Baseline in the ASAS Health Index at week 12.
To explore the Spinal mobility assessed by Bath Ankylosing Spondylitis Metrology Index (BASMI) linear scores.	Mean change from baseline in BASMI linear scores.
To explore the efficacy of Secukinumab 150 mg s.c. in achieving the ASAS40 response over time.	Proportion of patients fulfilling the ASAS40 criteria in each treatment group over time.
To explore the efficacy of Secukinumab 150 mg s.c. in achieving the ASAS20 response over time.	Proportion of patients fulfilling the ASAS20 criteria in each treatment group over time
To explore the efficacy of Secukinumab 150 mg s.c. in achieving the ASAS5/6 response over time.	Proportion of patients fulfilling the ASAS5/6 criteria in each treatment group over time.
To explore the efficacy of Secukinumab 150 mg s.c. assessed by hsCRP.	Mean change from baseline in hsCRP.
To explore the efficacy of Secukinumab 150 mg s.c. assessed by total BASDAI over time.	Mean change from baseline in total BASDAI score in each treatment group over time.
To explore the efficacy of Secukinumab 150 mg s.c. in achieving BASDAI 50 response over time.	Proportion of patients fulfilling BASDAI 50 response criteria in each treatment group over time.
To explore the efficacy of Secukinumab 150 mg s.c. in achieving ASAS partial remission response over time.	Proportion of patients fulfilling ASAS partial remission criteria in each treatment group over time
To explore the efficacy of Secukinumab 150 mg s.c. assessed by ASAS components, including: a. Patient's global assessment of disease activity b. Total spinal pain c. Inflammation as measured by the mean of BASDAI questions 5 and 6	Mean change from baseline for each treatment group in ASAS components including: a. Patient global disease activity b. Total spinal pain c. Inflammation (average of BASDAI questions 5 and 6) d. BASFI

d. Bath Ankylosing Spondylitis Functional Index (BASFI)	

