## 2.13 Other Exploratory analyses

All the exploratory efficacy evaluation will be performed on FAS population. Refer to [Table 1.2-1](#) of Section 1 for the list of exploratory endpoints.

The following exploratory efficacy variables will be summarized on the FAS for all applicable analysis visits unless otherwise specified.

1. Total ASAS-NSAID [Area Under Curve (AUC)] Score from treatment start with Secukinumab to a Secukinumab exposure of 12 weeks.
2. Total ASAS-NSAID [Area Under Curve (AUC)] Score From Week 4 to Week 16
3. Proportion of patients with no NSAID intake after Secukinumab exposure of 12 weeks
4. Proportion of patients with no NSAID intake at week 12.
5. Change from Baseline in the ASAS Health Index after Secukinumab exposure of 12 weeks
6. Change from Baseline in the ASAS Health Index at week 12
7. Change from baseline in BASMI
8. ASAS40 response
9. ASAS20 response
10. ASAS5/6 response
11. Change from baseline in hsCRP
12. Change from baseline in total BASDAI
13. BASDAI 50 response

14. ASAS partial remission
15. Change from baseline in ASAS components including:
  - Patient global disease activity
  - Total spinal pain
  - Inflammation (average of BASDAI questions 5 and 6)
  - BASFI
16. Change from baseline in ASDAS-CRP and ASDAS-ESR
17. ASDAS inactive disease as defined by  $ASDAS < 1.3$
18. ASDAS clinically important improvement (change in  $ASDAS \geq 1.1$ ) and major improvement (change in  $ASDAS \geq 2.0$ )
19. Reasons given in the patient diary on why he was not able to taper NSAIDs despite reduced spinal pain

All endpoints relating to exploratory objectives will be summarized descriptively. Summary statistics will include absolute frequencies and percentages for the categorical variables and the number of patients (n), minimum, mean, median and maximum for continuous variables. Change from baseline will also be presented for some exploratory variables based on the the endpoints mentioned in section 1 Table 1.2-1. Graphical representation will also be performed if required.

The following exploratory endpoints will also be summarized categorically as absolute and relative frequencies (proportions, %).

- Proportion of patients fulfilling ASAS20 criteria at week 4 for secukinumab 150 mg s.c. (delayed tapering) vs. week 20 in patients switching from placebo after weeks of secukinumab exposure.

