## 4 Change to protocol specified analyses

Not applicable.

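### The protocol requires hsCRP to be analysed on the log scale; the SAP specifies only a descriptive mean change and declares no departure

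*Protocol*

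**What the plan says.** **Protocol.** Section 9.5.2 lists change from baseline in hsCRP among the exploratory efficacy variables, then fixes the scale: "Variables such as hsCRP whose distribution is not anticipated to be normal will be transformed and analyzed on the loge scale". The next sentence delegates the rest: "All other details and analyses regarding the exploratory efficacy variables will be outlined in the statistical analysis plan". Section 9.5.1 gives an MMRM for continuous variables, with treatment regimen and visit as factors, weight and baseline score as covariates, and interactions of treatment and baseline with visit. Section 3.6.1.1 reports hsCRP from an earlier phase 3 trial as "significantly lower ratios of post-baseline to baseline hsCRP values": 0.40 for the i.v.-loaded 150 mg arm and 0.97 for placebo.

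**SAP.** Table 1.2-1 defines the hsCRP endpoint as "Mean change from baseline in hsCRP". Section 2.13 states: "All endpoints relating to exploratory objectives will be summarized descriptively", and lists "the number of patients (n), minimum, mean, median and maximum for continuous variables". Section 2.1 adds the standard deviation and quartiles for continuous data in general. Section 4, headed "Change to protocol specified analyses", reads "Not applicable".

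**The concern.** The protocol expects hsCRP to be non-normal and draws the usual consequence. The SAP, which the programmers follow, mentions neither the transformation nor a ratio, and its list of departures is empty. Two elements drop out: the log scale, and the step from summarising the variable to analysing it.

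At stake is how readable one objective result will be. Protocol 3.4 notes that the primary and key secondary endpoints all rest on patient report. On-treatment hsCRP is measured centrally and withheld from sites until database lock (protocol 6.4.10), so it is a useful independent reading of inflammation while NSAIDs are tapered. A mean change in mg/L weights patients by their absolute level and cannot be compared with the ratios the protocol uses as background.

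**Working it through.** **1. The two documents side by side**

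| Element | Protocol | SAP |
|---|---|---|
| Scale for hsCRP | loge, stated as a rule (9.5.2) | none named; the only logarithm in the SAP is inside the ASDAS-CRP formula (5.5.2) |
| Treatment of the variable | analysed (9.5.2) | summarised descriptively (2.13) |
| Statistics | left to the SAP | n, minimum, mean, median, maximum (2.13); SD and quartiles (2.1); no geometric mean or ratio |
| Model | MMRM for continuous variables (9.5.1) | ANCOVA for continuous endpoints expected to be normal; no rule for the others (5.4) |
| Declared departures | – | none (section 4) |

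The log rule comes before the sentence that hands the remaining details to the SAP, so the scale was not among the things left open.

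**2. Size.** The plan states no power, standard deviation or sample size for hsCRP, so there is no figure of its own to reproduce. What follows is an illustration.

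*From the documents:* ratios 0.40 and 0.97 (protocol 3.6.1.1); about 190 patients randomised 1:1:1, taken as 127 pooled secukinumab and 63 placebo.
*Assumed:* lognormal hsCRP with baseline median m = 7 mg/L; SD of log baseline s = 0.8 to 1.4; SD of log change c = 0.7 to 1.0; change independent of baseline.

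Log scale. The effect is ln(0.40/0.97) = −0.886, a geometric mean ratio of 0.41 whatever the baseline spread. Its standard error is c × √(1/127 + 1/63) = c × 0.154, that is 0.108 to 0.154.

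Raw scale. The expected difference in mean change is m × exp(s²/2) × exp(c²/2) × (0.40 − 0.97):
- s = 0.8, c = 0.7: 7 × 1.377 × 1.278 × (−0.57) = −7.0 mg/L
- s = 1.4, c = 1.0: 7 × 2.664 × 1.649 × (−0.57) = −17.5 mg/L

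So the same ratio gives raw differences 2.5 times apart (17.5/7.0), purely through the assumed spreads. Simulation (4,000 trials per setting; SD across trials in brackets; power from a Welch t-test):

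| s | c | Difference in mean change, mg/L | Difference in median change, mg/L | Share of absolute change in the top 6 of 63 placebo patients | Power, raw | Power, log |
|---|---|---|---|---|---|---|
| 0.8 | 0.7 | −6.99 (1.77) | −3.36 (0.70) | 45% | 99% | 100% |
| 0.8 | 1.0 | −9.14 (3.74) | −3.12 (0.96) | 52% | 90% | 100% |
| 1.1 | 0.7 | −9.34 (3.15) | −3.19 (0.68) | 53% | 95% | 100% |
| 1.1 | 1.0 | −12.09 (6.80) | −2.84 (0.85) | 57% | 78% | 100% |
| 1.4 | 0.7 | −13.86 (7.58) | −3.07 (0.70) | 60% | 86% | 100% |
| 1.4 | 1.0 | −17.56 (13.94) | −2.62 (0.81) | 63% | 63% | 100% |

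The raw mean is unstable and the median is not. Neither gives the ratio the protocol asks for. The power columns express lost precision only, because the SAP plans no test of hsCRP.

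**The case against.** The best reply is that the SAP is silent, not contrary. SAP section 1 says the data are analysed according to protocol section 9, which contains the log rule. The protocol itself uses the label of change from baseline next to that rule, so the label does not prove a raw-scale analysis. This stands in part: the rule is lost by omission, and the text does not support an inference that the sponsor deliberately reversed it. But Table 1.2-1 and 2.13 describe the output concretely, and none of it is on the log scale. If the general pointer prevails, the SAP is inconsistent with itself; the wording needs repair either way.

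Four further points stand.
- A reader might infer that hsCRP will be reported only through an outlier-driven mean. Not so: median, quartiles and extremes would show the skew.
- A reader might take the power figures as a loss this trial will suffer. No hsCRP test is planned and the spreads are assumed. The ratios come from a trial with i.v. loading, read at Week 16; here loading is s.c., and at Week 12 the early-tapering arm has had only 8 weeks of secukinumab.
- hsCRP is not the only objective evidence. Log CRP enters ASDAS-CRP, CRP is a domain of ASAS 5/6, and ESR and BASMI are also measured. These are not full substitutes: ASDAS-CRP mixes in patient-reported items and ESR is read at the site. Nor is CRP masking absolute, since local testing is allowed for safety.
- Whether the protocol makes the MMRM mandatory for an exploratory variable is arguable. The log scale is required; a modelled comparison with placebo is the better choice but goes a step beyond repairing the mismatch.

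**Conclusion.** The mismatch is real and rests on the text alone: a log-scale rule in protocol 9.5.2, a descriptive mean change without transformation in SAP Table 1.2-1 and 2.13, and no departure declared in section 4. Its consequence is minor. As written, the exploratory hsCRP result would be a change in mg/L that is sensitive to a few high values, carries no contrast between arms and is not comparable with the cited 0.40 and 0.97.

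The stronger conclusion that the trial's findings are at risk is not supported: hsCRP lies outside H1 to H11, so no confirmatory hypothesis, type I error rate or sample size changes. The numerical illustration depends on an assumed lognormal shape, baseline median and spreads; the mismatch does not.

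**What to change.** In SAP Table 1.2-1 and section 2.13, define the hsCRP endpoint as loge(post-baseline/baseline). Report back-transformed geometric mean ratios with 95% confidence intervals by arm and versus placebo, preferably from the MMRM of protocol 9.5.1 with log baseline as the covariate. Comparisons with placebo should stop at Week 16, when that arm switches to secukinumab. The mg/L summary can stay as a supplement. If the raw scale is intended, say so in section 4 and justify it.

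The cost is a few lines of SAP text and one further use of a model type for which SAP 5.4 already gives code. The small downside is that the log scale needs a stated rule for values below the assay limit. The SAP's history entry predates database lock, and the change should be made before lock too.

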9.5.3 Safety variables

Adverse events

Treatment emergent adverse events (events started after the first dose of study treatment or events present prior to the first dose of study treatment but increased in severity based on preferred term) will be summarized.

AEs will be summarized by presenting, for each treatment group, the number and percentage of subjects having any AE, having an AE in each primary system organ class and having each individual AE (preferred term). Summaries will also be presented for AEs by severity and for study treatment related AEs. If a subject reported more than one adverse event with the same preferred term, the adverse event with the greatest severity will be presented. If a subject reported more than one adverse event within the same primary system organ class, the subject will be counted only once with the greatest severity at the system organ class level, where applicable. Serious adverse events will also be summarized.

These summaries will be presented separately by study periods, i.e. Weeks 1-16 and after Week

As appropriate, the incidence of AEs will be presented per 100 subject years of exposure.

Separate summaries will be provided for death, serious adverse event, other significant adverse events leading to discontinuation and adverse events leading to dose adjustment (including study treatment discontinuation).

A graphical display of relative frequencies within system organ classes and relative risks, as appropriate, will be presented.

When adjudication is required of major cardiovascular events, a summary of those types of events as reported by the investigator and confirmed by adjudication will be provided.

Laboratory data

The summary of laboratory evaluations will be presented for three groups of laboratory tests (hematology, serum chemistry and urinalysis). Descriptive summary statistics for the change from baseline to each study visit will be presented. These descriptive summaries will be presented by test group, laboratory test and treatment group. Change from baseline will only be summarized for subjects with both baseline and post baseline.

For each parameter, the maximum change from baseline within each study period will be evaluated analogously.

In addition, shift tables will be provided for all parameters to compare a subject's baseline laboratory evaluation relative to the visit's observed value. For the shift tables, the normal laboratory ranges will be used to evaluate whether a particular laboratory test value was normal, low, or high for each visit value relative to whether or not the baseline value was

Protocol No. CAIN457FDE03

normal, low, or high. These summaries will be presented by laboratory test and treatment group. Shifts will be presented by visit as well as for most extreme values post-baseline.

Vital signs

Analysis of the vital sign measurements using descriptive summary statistics for the change from baseline for each post-baseline visit will be performed. These descriptive summaries will be presented by vital sign and treatment group. Change from baseline will only be summarized for subjects with both baseline and post-baseline values.

HLA-B27

Human Leukocyte Antigen-B27 (HLA-B27) will be summarized at baseline and listed.

9.5.4 Resource utilization

Not applicable.

9.5.5 Pharmacokinetics

Not applicable.

9.5.6 Pharmacogenetics/pharmacogenomics

Not applicable.

9.5.7 Biomarkers

Not applicable.

9.5.8 PK/PD

Not applicable.

9.6 Interim analyses

Not applicable.

9.7 Sample size calculation

All sample size and power considerations are performed using EAST 6.

The sample size was calculated based on the phase III results of the MEASURE2 study, which used the same dose and loading regimen as will be applied in this trial. Under the assumption of 56.9% ASAS20 responders in the Secukinumab (delayed tapering) group and 27.0% in the placebo group, a sample size of 62 patients per group is required to have 90% power to show superiority of Secukinumab over placebo at a two sided $\alpha=5\%$.

For the comparison of the the early tapering group at week 16 vs. placebo, the same treatment effect is expected, leading to the same sample size. To compensate for some dropout and other protocol deviations, the sample size will be increased to 68 per arm. The total sample size of this trial will thus be 204. At the time of writing this amendment, about 190 patients have been recruited into this trial and it seems unlikely that a sample > 200 can be recruited within reasonable time. With this sample size, the (newly introduced) comparison of pooled

Secukinumab groups vs. placebo, the trial would still have almost 80 % (78%) power if the placebo response was somewhat higher (35%) than originally assumed...

Other secondary endpoints

It will be assumed that the amount of NSAID reduction observed in the etanercept SPARSE trial (Dougados et al. 2014), of 63.9 vs. baseline (etanercept) and 36.6 for placebo, with an estimated standard deviation of 40 will be seen in this trial for both Secukinumab groups versus placebo. Based on this assumption both secukinmab groups will have >90% power to show superiority over placebo for NSAID reduction.

For the total BASDAI parameter, 62 patients per treatment group should yield a power of approximately 91%, assuming a a treatment difference of 1.8 with a standard deviation of 2.8 (van der Heijde 2006). For SF-36 PCS, 62 patients per treatment group yield a power of approximately 87.5%, assuming mean change of 6.9 on both Secukinumab regimen and mean change of 1.6 on placebo with common standard deviation of 8.7 (Davis 2007).

10 Ethical considerations

Study documentation, record keeping and retention of documents

Each participating site will maintain appropriate medical and research records for this trial, in compliance with Section 4.9 of the ICH E6 GCP, and regulatory and institutional requirements for the protection of confidentiality of patients. As part of participating in a Novartis-sponsored study, each site will permit authorized representatives of the sponsor(s) and regulatory agencies to examine (and when required by applicable law, to copy) clinical records for the purposes of quality assurance reviews, audits and evaluation of the study safety and progress.

Source data are all information, original records of clinical findings, observations, or other activities in a clinical trial necessary for the reconstruction and evaluation of the trial. Examples of these original documents and data records include, but are not limited to, hospital records, clinical and office charts, laboratory notes, memoranda, patients' diaries or evaluation checklists, pharmacy dispensing records, recorded data from automated instruments, copies or transcriptions certified after verification as being accurate and complete, microfiches, photographic negatives, microfilm or magnetic media, x-rays, and patient files and records kept at the pharmacy, at the laboratories, and medico-technical departments involved in the clinical

Data collection is the responsibility of the clinical trial staff at the site under the supervision of the site Principal Investigator. The study case report form (CRF) is the primary data collection instrument for the study. The investigator should ensure the accuracy, completeness, legibility, and timeliness of the data reported in the CRFs and all other required reports. Data reported on the CRF, that are derived from source documents, should be consistent with the source documents or the discrepancies should be explained. All data requested on the CRF must be recorded. Any missing data must be explained. Any change or correction to a paper CRF should be dated, initialed, and explained (if necessary) and should not obscure the original entry. For electronic CRFs an audit trail will be maintained by the system. The investigator should retain records of the changes and corrections to paper CRFs.

The investigator/institution should maintain the trial documents as specified in Essential Documents for the Conduct of a Clinical Trial (ICH E6 Section 8) and as required by applicable regulations and/or guidelines. The investigator/institution should take measures to prevent accidental or premature destruction of these documents.

Essential documents (written and electronic) should be retained for a period of not less than fifteen (15) years from the completion of the Clinical Trial unless Sponsor provides written permission to dispose of them or, requires their retention for an additional period of time because of applicable laws, regulations and/or guidelines.

Confidentiality of study documents and patient records

The investigator must ensure anonymity of the patients; patients must not be identified by names in any documents submitted to Novartis. Signed informed consent forms and patient enrollment log must be kept strictly confidential to enable patient identification at the site.

